4.3.8. Visit Windows

Visit windows, which will be used to associate assessments with a scheduled visit, will be used only for summarizing data by visit. The windows for scheduled assessments are shown in [Table 3: Visit Windows for Monthly and Quarterly Assessments \(Monthly and Quarterly Visit, Lab and PGA\) \(Monthly and Quarterly Visit, Lab and PGA\)](#), [Table 4 \(BMD\)](#), [Table 5 \(electrocardiogram \[ECG\]\)](#), [Table 6 \(EHP-30\)](#), [Table 7 \(EHP work domain and EQ-5D-5L\)](#), [Table 8 \(PGIC\)](#), [Table 9 \(Endometriosis Biopsy\)](#), [Table 10 \(Mammogram\)](#), and [Table 11 \(eDairy\)](#) respectively. For safety assessments, the study day will be used to determine the associated visit window. There will be no separation of data from the pivotal phase 3 and extension study. For example, if an assessment in the extension study falls in the Week 24 visit window, it will be summarized as Week 24.

If the results from more than one assessment are within a given visit window, the non-missing result from the assessment closest to the target date will be used. If two assessments are equally close to the target day, the earlier assessment will be used. For summaries of shift from Baseline in safety parameters, all values will be considered for these analyses.

Table 3: Visit Windows for Monthly and Quarterly Assessments (Monthly and Quarterly Visit, Lab and PGA)

Visit	Start Day	Target Day	End Day
Week 4 ^a	1(2 ^b)	29	43
Week 8	44	57	71
Week 12	72	85	99
Week 16	100	113	127
Week 20	128	141	155
Week 24	156	169	183
Week 28	184	197	211
Week 32	212	225	239
Week 36	240	253	267
Week 40	268	281	295
Week 44	296	309	323
Week 48	324	337	351
Week 52	352	365	411
Week 65	412	456	502
Week 78	503	547	593
Week 91	594	638	684
Week 104	685	731	Date of last dose + 6 days
Safety Follow-Up ^c	Date of last dose + 7 days	Date of last dose + 30 days	Date of last dose + 60 days

^a Start day of Week 4 for study day 1 includes only post-Baseline assessments that occurred after the first dose.

^b For Patient Global Assessments (PGAs), the start day of the Week 4 visit window begins at Day 2.

^c The safety Follow-Up visit window will be restricted to assessments prior to the date of initiation of another investigational agent or hormonal therapy affecting the hypothalamic- pituitary- gonadal axis or surgical intervention for endometriosis-associated pain.

Table 4: Visit Windows for Bone Mineral Density Assessments

Visit	Start Day	Target Day	End Day

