Week 44	X ₁₁	(X ₁₁ - 34) to ≤ X ₁₁
Week 48	X ₁₂	(X ₁₂ - 34) to ≤ X ₁₂
Week 52	X ₁₃	(X ₁₃ - 34) to ≤ X ₁₃
Week 65 ^g	X ₁₄	(X ₁₄ - 56) to ≤ X ₁₄
Week 78 ^g	X ₁₅	(X ₁₅ - 56) to ≤ X ₁₅
Week 91 ^g	X ₁₆	(X ₁₆ - 48) to ≤ X ₁₆
Week 104 ^g	X ₁₇	(X ₁₇ - 51) to ≤ X ₁₇
Week104/EOT ^c	X ₁₇	Maximum [OLE start day ^c , (X ₁₇ - 34)] to ≤ X ₁₇ or PAP ^f

Abbreviation: EOT = end of treatment, OLE = open label extension.

Error! Reference source not found. Refer to **Error! Reference source not found.** Table 3 for target study day for Weeks 4, 8, 12, 16, 20, 24, 28, 32, 36, 40, 44, 48, 52, 65, 78, 91, 104 and safety Follow-Up.

^b The target study day for Week 24 is defined as date of last dose of randomized study treatment in pivotal phase 3 study. The Week 24 assessment period is defined as the 35 days up to and including the date of last dose of randomized study treatment in pivotal phase 3 study, which should occur on the day prior to the Week 24 visit.

^c OLE start day = day of first dose administered of extension study treatment.

^e The target study day for Week 104/EOT for purposes of visit window calculations is defined as date of last dose of study treatment in the extension study.

^f If the last 35 calendar days prior to and including date of last dose of study drug are not entirely within an eDiary collection period, then days of the pain assessment period (PAP) will be determined as follows: (1) if the date of last dose occurs during the eDiary collection period, the PAP will be the last 35 days which are counted during up to two eDiary collection periods immediately prior to and including date of last dose of study drug (2) if the date of last dose occurs outside of the eDiary collection period, the PAP will be the last 35 days which are counted during up to two eDiary collection period(s) immediately prior to but not including date of last dose of study drug.

^g: For Week 65, Week 78, Week 91 and Week 104, only data collected within eDiary cycles required by protocol is included in the analysis.

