7.2.4. Definitions Related to Numerical Rating Scale Pain Scores and Analgesic Use

Dysmenorrhea NRS Scores

Dysmenorrhea NRS pain scores are pain scores reported in the eDiary on days that the patient reports she is bleeding. Non-menstrual pelvic pain NRS pain scores are those pain scores reported in the eDiary on days that the patient reports she is not bleeding.

Baseline Assessment of NRS Pain Scores and Analgesic Use

Pivotal phase 3 study baseline NRS pain scores will be used as baseline NRS pain scores in the extension study analyses. Baseline NRS pain scores for DYS and NMPP are the averages of the respective eDiary pain scores reported during the baseline pain assessment period.

Pivotal phase 3 study baseline analgesic use for pelvic pain will be used as baseline analgesic use in the extension study analyses. It is the average daily pill count as reported in the eDiary during the pivotal phase 3 study baseline pain assessment period. The baseline average daily pill count will be calculated separately for Tier 1 and Tier 2 analgesics.

Week 52 and Week 104/EOT Assessment of NRS Pain Scores and Analgesic Use

The Week 52 pain scores for DYS and NMPP are the averages of the respective eDiary pain scores reported during the Week 52 pain assessment period (PAP), defined as the last 35 calendar days of extension study treatment immediately prior to Week 52. For patients with extension study treatment duration less than 35 days, Week 52 PAP is defined as the days between the first dose of extension study drug and date of last dose of extension study drug.

Week 52 analgesic use for pelvic pain is the average daily pill count as reported in the eDiary during the Week 52/ PAP. The average daily pill count will be calculated separately for Tier 1 and Tier 2 analgesics for Week 52.

Since eDiary is not required to report out of the eDiary collection cycle, ie. Week 53 - 57, Week 66 - 70, Week 79 - 84 and Week 92 - 97, study days in those periods would not be included in the Week 104/EOT pain assessment period or analgesic use for primary endpoints analyses.

The Week 104/EOT pain scores for DYS and NMPP are the averages of the respective eDiary pain scores reported during the Week 104/EOT PAP, defined as

- If the last 35 calendar days prior to and including date of last dose of extension study drug are entirely within an eDiary collection period, then the PAP will be the last

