35 calendar days immediately prior to and including the date of last dose of study drug;

- If the date of last dose occurs outside of the eDiary collection period or there are not 35 calendar days prior to the last dose of extension study drug from the eDiary collection period that includes the last dose, the PAP will be the last 35 days in the eDiary collection day on or prior to the last dose of study drug, from the last one or two eDiary collection periods.
- If the last 35 calendar days prior to and including date of last dose of study drug are not entirely within an eDiary collection period:
 - if the date of last dose occurs during the eDiary collection period, the PAP will be the last 35 days which are counted during up to two eDiary collection periods immediately prior to and including date of last dose of study drug
 - if the date of last dose occurs outside of the eDiary collection period, the PAP will be the last 35 days which are counted during up to two eDiary collection period(s) immediately prior to but not including date of last dose of study drug

Week 104/EOT analgesic use for pelvic pain is the average daily pill count as reported in the eDiary during the Week 104/EOT PAP. The average daily pill count will be calculated separately for Tier 1 and Tier 2 analgesics for Week 104/EOT.

NRS pain scores and analgesic use during PAP of each of other study weeks will be calculated for efficacy analysis by visit. Pain scores for DYS and NMPP are the averages of the respective eDiary pain scores reported during each individual PAP. Analgesic use for pelvic pain is the average daily pill count as reported in the eDiary during each individual PAP.

For Week 65, 78, 91 and 104, PAP is defined as the total days of ed diary collection period immediately prior to respective week. For Week 28 to Week 48, PAP is defined as the last 35 calendar days of extension study treatment immediately prior to respective week. For patients with extension study treatment duration less than 35 days, PAP is defined as the days between the first dose of extension study drug and date of last dose of extension study drug. **Definition of Increased Use of Analgesics**

The definition of increased analgesic use in pivotal phase 3 studies will be applied to this extension study. Protocol-specified analgesic medications for endometriosis-associated pain will be analyzed based on the following categories:

- Tier 1
 - Ibuprofen (200 mg)
- Tier 2:

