7.2.6. Derivation of Responder Status at Week 52, Week 104/EOT and Missing Data Handling Rules

For the primary efficacy analysis, both primary endpoints will incorporate the missing data handling rules at Week 52, Week 104/EOT as follows (Table 14, Table 15 and Figure 2):

- For patients missing eDiary for all visits in the extension study, their Baseline/Week 24 responder status from the pivotal phase 3 study will be carried over as their responder status to Week 52, Week 104/EOT.
- For patients who have any pain score entries in eDiary in the extension study, responder status for DYS and NMPP will be derived as follows:
 - For DYS, the responder status will be defined using the following rules taking analgesic use into consideration (Table 14):
 - If there are at least 2 days of DYS NRS scores reported in the eDiary, then the average will be calculated and used in the assessment of the DYS responder status. Requiring a minimum of 2 days of DYS NRS scores is considered reasonable since a typical menstrual cycle has bleeding days ranging from 3 to 7 days.
 - If there are < 2 days of NRS scores for DYS reported in the eDiary, then the following scenarios will be considered:
 - If no DYS scores are reported in the eDiary, then the data collected on the menstruation eCRF will be considered as follows:
 - If no menstruation is reported on the eCRF, then the average DYS score will be set as 0;
 - Otherwise, if any menstruation days are reported on the eCRF, then the average DYS score will be set as missing and will be imputed using a mixed-effects model.

- If only one DYS score is reported in the eDiary, then the data collected on the menstruation eCRF will be considered as follows:
 - If no more than one menstruation day is reported on the eCRF, then the observed DYS score will be taken as the average DYS score;
 - If more than one menstruation day is reported on the eCRF, then the average DYS score will be considered missing and will be imputed using a mixed-effects model.
- For NMPP, the responder status will be defined using the following rules, taking analgesic use into consideration (Table 15):
 - If there are at least 14 days of scores for NMPP reported in the eDiary, then the average NMPP score will be used in the assessment of the NMPP responder status. Requiring minimum 14 days of NMPP scores is considered reasonable since this corresponds to at least half of the non-menstrual days from a typical 28-day menstrual cycle.

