 - If there are less than 14 days of NMPP scores in the eDiary, then the average NMPP score will be considered missing and will be imputed using predicted values from a mixed-effects model.

Table 14: Missing Data Handling Rules for Average Dysmenorrhea NRS Score at Week 52, Week 104/ EOT

Number of Days with DYS Scores Reported in eDiary	Menstruation Status per eCRF	Average DYS Score Status	Responder Status ^a
Missing all eDiary data during extension study			
n/a	n/a	n/a	Baseline/Week 24 responder status from pivotal phase 3 study
Having at least one eDiary data during extension study			
≥ 2 days	n/a	Observed	Based on observed change from baseline and analgesic use
1 day	No more than 1 menstruation day reported	Observed	Based on observed change from baseline and analgesic use
	More than 1 menstruation day reported	Missing (to be imputed from mixed-effects model)	Based on imputed change from baseline and analgesic use
0 days	No menstruation days reported	Assigned as 0	Based on change from baseline and analgesic use
	At least 1 menstruation day reported	Missing (to be imputed from mixed-effects model)	Based on imputed change from baseline and analgesic use

Abbreviations: eCRF = electronic case report form; eDiary = electronic diary; n/a = not applicable.

^a Determined by comparing the observed (or imputed) change from baseline to the responder threshold and by examination of change from baseline in analgesic use.

[figure not shown]
Table 15: Missing Data Handling Rules for Average Non-Menstrual Pelvic Pain NRS Score at Week 52, Week 104/EOT

Number of Days with NMPP Scores Reported in eDiary	Average NMPP Score Status	Responder Status ^a
Missing all eDiary data during extension study		
n/a	n/a	Baseline/Week 24 responder status from pivotal phase 3 study
At least one eDiary data during extension study		
≥ 14 days	Observed	Based on observed change from baseline and analgesic use
< 14 days	Missing (to be imputed from mixed-effects model)	Based on imputed change from baseline and analgesic use

Abbreviations: eDiary = electronic diary; n/a = not applicable; NMPP = non-menstrual pelvic pain.

^a Determined by comparing the observed (or imputed) change from baseline to the responder threshold and by examination of change from baseline in analgesic use.

Figure 2: Visual Depiction of the Missing Data Handling Rules and Determination of Responder Status for the Primary Efficacy Endpoints

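### SAP Section 7.2.4 and Table 11 conflict on the Week 52 pain assessment period: irreconcilable for patients with under 35 days of extension treatment, ambiguous for other patients who stopped before Day 365

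*SAP*

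**What the plan says.** Section 7.2.4 describes the Week 52 period as "defined as the last 35 calendar days of extension study treatment immediately prior to Week 52". For patients with less than 35 days of extension treatment it adds that "Week 52 PAP is defined as the days between the first dose of extension study drug and date of last dose of extension study drug". For Weeks 28 to 48 the same section says "PAP is defined as the last 35 calendar days of extension study treatment immediately prior to respective week", again followed by the short-exposure rule.

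Table 11 (Section 4.3.8) defines the Week 52 window as X13 minus 34 to X13. Its note sends the reader to "Table 3 for target study day for Weeks 4, 8, 12, 16, 20, 24, 28, 32, 36, 40, 44, 48, 52", and the Table 3 row reads "Week 52 352 365 411", so X13 is Day 365. The Week 52 row contains no last-dose term. The last-dose anchor is stated for a different row, in a note that begins: "The target study day for Week 104/EOT for purposes of visit window calculations is defined as date of last dose of study treatment in the".

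The choice of window feeds the missing-data rules of Section 7.2.6. For non-menstrual pelvic pain (NMPP): "If there are less than 14 days of NMPP scores in the eDiary, then the average NMPP score will be considered missing", and it is then imputed from the mixed model. For dysmenorrhea (DYS) with no diary scores: "If no menstruation is reported on the eCRF, then the average DYS score will be set as 0"; if menstruation is reported, the score is imputed.

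**The concern.** The Week 52 responder rates for DYS and NMPP are primary endpoints, and two parts of the SAP can send a programmer to different diary days for the same patient. No sentence says which part governs.

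Followed literally, the short-exposure rule reports pain from roughly Weeks 24 to 29 as Week 52 pain. The parallel rule assigns the same few weeks to each visit from Week 28 to Week 48. One short period would then supply seven visits (28, 32, 36, 40, 44, 48 and 52). If those values feed the imputation model of Section 7.2.7, they enter as observed data, against Section 4.4.1, which says by-visit endpoints use observed records without imputation.

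For patients who stopped later but before Week 52, one reading keeps their last on-treatment pain as the Week 52 value. The other sends many of them to imputation or to the DYS zero rule. In an open-label study, that choice should not be left until data are visible.

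**Working it through.** **Inputs.** Week 52 target day 365, Week 24 target day 169, and the targets for Weeks 28 to 36 (197, 225, 253) are from Table 3. The 34-day look-back is from Table 11. The permitted delay of up to 10 days in starting extension drug is from Section 2.1. Assumption: extension treatment starts on Day 169, or Day 179 with the full delay.

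**Table 11 window.** 365 − 34 = 331, so Days 331 to 365, which is 365 − 331 + 1 = 35 days. The length agrees with Section 7.2.4; the anchor is what differs.

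**Under 35 days of extension treatment.** The longest such exposure is 34 days.
- Start on Day 169: last day 169 + 33 = 202. Gap to the window: 331 − 202 = 129 days.
- Start on Day 179: last day 179 + 33 = 212. Gap: 331 − 212 = 119 days.

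The text period and the Table 11 window share no day, however the 35-day phrase is read.

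**The same rule at Weeks 28 to 48.** With a Day 169 start, Table 11 gives Days 169 to 197 for Week 28 (the later of 169 and 197 − 34 = 163), Days 191 to 225 for Week 32, and Days 219 to 253 for Week 36. A short-exposure patient can have on-treatment days in the first two. From Week 36 onward she has none, even with the delayed start (212 < 219), yet the text still assigns her a period.

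**35 days or more, stopped before Day 365.** If the text means the last 35 on-treatment days, its period for last-dose day d is d − 34 to d.

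| Last dose (day) | Text period | Days shared with 331–365 |
|---|---|---|
| 300 | 266–300 | 0 |
| 330 | 296–330 | 0 |
| 343 | 309–343 | 13 |
| 344 | 310–344 | 14 |
| 364 | 330–364 | 34 |
| 365 | 331–365 | 35 |

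Counting on-treatment diary days only, the shared days are also all that Table 11 leaves. This has two consequences:
- **NMPP.** A stop by Day 343 leaves at most 13 days, so the score is imputed under Table 11. The on-treatment reading can use up to 35 observed days.
- **DYS.** A stop by Day 330 leaves no days, so the score becomes 0 or is imputed under Table 11. The on-treatment reading can use observed scores if she bled.

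**Off-treatment diary days.** Section 2.1 continues the diary for about 30 days after treatment, and the Week 52 row of Table 11 does not exclude those days. A stop on Day 330 could put Days 331 to 360, up to 30 off-treatment days, into the window.

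**Analgesic component.** Section 7.2.4 counts pills within the same period. Table 13 has a fallback only for patients with no extension diary data at all, so it does not cover a patient with diary data but none in the window.

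**Completers to Day 365.** Both definitions give Days 331 to 365. Taking the text strictly as days before Week 52 gives Days 330 to 364, a one-day shift.

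**The case against.** The best defence is that the Section 7.2.4 phrase ties the 35 days to Week 52 itself and so describes the Table 11 window limited to treatment days. The SAP is explicit when it wants an end-of-treatment anchor: it names the endpoint Week 104/EOT and refers to last dose. The Week 52 endpoint carries no such label. Its imputation rules would have little to do if last on-treatment data always filled the slot. Section 7.1.2 also directs change scores to the Section 4.3.8 windows, which argues against carried-forward values entering the mixed models.

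Much of this stands. For patients with at least 35 days of extension treatment, the text is ambiguous rather than contradictory. It does not rescue the short-exposure sentence, which makes sense only if the period follows last dose. Section 7.1.2 concerns continuous change scores, not responder status.

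One could also argue that Section 4.3.8 restricts visit windows to by-visit summaries, so that Table 11 does not govern the primary endpoint. But Table 11 contains the Week 104/EOT row, and its notes repeat the primary-endpoint period rules.

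A reader might infer that the endpoint changes for every patient who stopped before Week 52. The documents do not support that. Patients with no extension diary data keep their Week 24 status either way (Section 7.2.6). Responder status is a threshold result and can agree under both windows, especially for stops on Days 344 to 364, where 14 to 34 days are shared. A patient without bleeding can have DYS set to 0 under either window.

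Finally, the study is single-arm and descriptive, so no test or error rate depends on this, and the Week 104/EOT endpoints do not use this window.

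**Conclusion.** The conflict is real and concerns a primary endpoint. It is explicit for patients with under 35 days of extension treatment, where the two definitions lie at least 119 days apart given a start between Days 169 and 179. For longer-treated patients who stopped before Day 365, the wording allows two windows; whether the score is observed, imputed or set to 0 can differ, but responder status need not. Completers are unaffected apart from a possible one-day shift.

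The effect on the responder rate cannot be computed. It is the affected fraction times the gap in responder proportion between the two derivations, and the SAP gives neither. A reader might assume 15 to 25% early stoppers and a 20-point gap, giving 0.15 × 20 = 3 to 0.25 × 20 = 5 points. Or they might set 100% responders under the DYS zero rule against 60% on last observed data, giving 0.15 × 40 = 6 to 0.25 × 40 = 10 points. Neither range has a source in the SAP. The second also needs every early stopper to have no menstruation on the eCRF, a sufficient reduction from baseline and no increase in analgesic use. These ranges should not be cited as the size of the problem.

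The correction is still needed: as written, the short-exposure rule labels pain from around Weeks 24 to 29 as Week 52 pain.

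**What to change.** Before database lock, use one definition for the Week 52 and Week 28 to 48 periods:
- Adopt Table 11's study-day windows restricted to on-treatment days, and say so in Section 7.2.4.
- Delete the two short-exposure sentences for these visits.
- Send patients without enough data in the window through Sections 7.2.6 and 7.2.7.
- State how the analgesic component and the DYS zero rule apply to a patient who has extension diary data but no on-treatment days in the window.
- Say whether the Week 52 window includes the target day, which removes the one-day shift.

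If a last-on-treatment result is wanted, report it separately under the label Week 52/EOT.

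The cost is SAP wording and the matching programming specification; no new data are needed. The downside is that more early stoppers will be model-imputed at Week 52, so the rate leans more on the mixed model. The separate Week 52/EOT version would show how much that matters.

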 - Tramadol (37.5 mg)/Paracetamol (325 mg)
 - Tramadol (50 mg)
 - Codeine (30 mg)
 - Codeine (30 mg)/Paracetamol (300 mg)
 - Codeine (30 mg)/Paracetamol (500 mg)

- Codeine (15 mg)/Paracetamol (500 mg)
- Hydrocodone (5 mg)/Paracetamol (325 mg)

The Tier 2 analgesics prescribed for use in the study was country specific. Patients will record their use of these medications in an eDiary every day until Week 52 and after Week 52, eDiary scores will be entered over four eDiary collection cycles on following schedules: Week 57 to the Week 65 visit, Week 71 to the Week 78 visit, Week 85 to the Week 91 visit, and Week 98 to the Week 104 visit. This will include the information on medication name, dosage, usage of medication (eg, for endometriosis-associated pelvic pain or not), and total number of pills taken. The percent change in analgesic use between the pivotal phase 3 study baseline and Week 52 will be calculated as absolute change in analgesic use from pivotal phase 3 study baseline to Week 52 divided by pivotal phase 3 study baseline analgesic use. The percent change in analgesic use between the pivotal phase 3 study baseline and Week 104/EOT will be calculated as absolute change in analgesic use from pivotal phase 3 study baseline to Week 104/EOT divided by pivotal phase 3 study baseline analgesic use. For the primary endpoints of DYS and NMPP, patients will be considered as non-responders if they have an increase in rescue analgesic use as specified in Table 13.

Table 13: Effect of Protocol-Specific Analgesic Medication Use for Endometriosis-Associated Pain on Responder Status at Week 52, Week 104/EOT

Analgesic Use for EAP at Pivotal phase 3 study Baseline	Tier 1 Analgesic Use for EAP	Tier 2 Analgesic Use for EAP	Analgesic Responder Status ^a
Missing all eDiary data during extension study			
n/a	n/a	n/a	Baseline/Week 24 analgesic responder status from pivotal phase 3 study
At least one eDiary data during extension study			
No analgesic use	Any use	OR Any use	Non-responder
	No use	AND No use	Responder
Used Tier 1 analgesic only	Use increased > 15% from baseline	AND No use or any use	Non-responder
	Any use or no use	AND Any use	
	Use stopped, decreased, or stable	AND No use	Responder
Used Tier 2 analgesic only	Any use or no use	AND Use increased > 15% from baseline	Non-responder
	Any use	AND Use is stable	
	No use	AND Use stopped, decreased, or stable	Responder
	Started use	AND Use stopped or decreased	

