7.3.3. Analgesic use

Protocol-specified analgesics (see section 7.2.4) for endometriosis-related pain will be analyzed. Proportion of patients not using protocol-specified opioids for endometriosis-associated pain at Week 52, and Week 104/EOT will be presented by pivotal phase 3 study treatment group and by visit. Proportion of patients not using protocol-specified analgesics for endometriosis-associated pain at Week 52, and Week 104/EOT will be presented by pivotal phase 3 study treatment group and by visit. Two-sided 95% CIs for the proportions will be generated based on Clopper-Pearson exact binomial.

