7.3.5. Change from Baseline in Functional Impairment on sB&B Scale

The daily eDiary completed by patients includes assessments of endometriosis-associated pain by the sB&B scales for DYS, pelvic pain, and dyspareunia. The dysmenorrhea and dyspareunia scales have possible scores of 0 to 4, while the pelvic pain scale has possible scores of 0 to 3, as outlined in Table 19.

Table 19: Subject Modified Biberoglu and Behrman Scales for Dysmenorrhea, Pelvic Pain, and Dyspareunia

Dysmenorrhea	Pelvic Pain	Dyspareunia	Numerical Score
No pain	No pain	No pain	0
Mild	Mild	Mild	1
Moderate	Moderate	Moderate	2
Severe	Severe	Severe	3
Did not Menstruate	--	No Intercourse	4

The mean sB&B for DYS during the Week 52, Week 104/EOT pain assessment period will be the average over the days when the DYS response was something other than “Did not menstruate.” If the patient reports “Did not menstruate” for all days of the pain assessment period, then the mean sB&B score will be imputed as 0.

The mean sB&B for NMPP during the Week 52, Week 104/EOT pain assessment period, derived from the sB&B for pelvic pain, will be the average of the scores reported for days on which a patient reports she did not menstruate. Mean change of sB&B for NMPP and percent change from baseline will be presented by visit by treatment group.

The mean sB&B for dyspareunia during the Week 52, Week 104/EOT pain assessment period will be the average over the days when the dyspareunia response was something other than “No intercourse.” Mean change of sB&B for dyspareunia and percent change from baseline will be presented by visit by pivotal phase 3 study treatment group. Additionally, the following will be summarized for patients who reported one or more day on which they had vaginal sexual intercourse during a given time interval; the percentage of patients whose maximum dysmenorrhea score was severe, moderate, mild, and none during the specified time interval; the percentage of patients whose maximum dysmenorrhea score was severe or moderate and mild or none during the specified time interval.

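### By-visit pain assessment periods lengthen from 35 days at Week 52 to 49–57 days at Weeks 65–104, so the by-visit no-analgesic and no-opioid proportions are not comparable across Week 52

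*SAP*

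**What the plan says.** The Week 52 PAP is "defined as the last 35 calendar days of extension study treatment immediately prior to Week 52" (SAP 7.2.4). For the earlier extension visits, "For Week 28 to Week 48, PAP is defined as the last 35 calendar days of extension study treatment immediately prior to respective week". Table 11 (section 4.3.8) gives the same length, X − 34 to X, at Weeks 8–24 and 32–52. Week 4 is shorter (Day 1 to X), and Week 28 may start no earlier than the first extension dose.

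After Week 52 the rule changes: "For Week 65, 78, 91 and 104, PAP is defined as the total days of ed diary collection period immediately prior to respective week". Table 11 sets these rows at X − 56, X − 56, X − 48 and X − 51, and its footnote g adds that "only data collected within eDiary cycles required by protocol is included in the analysis". Week 104/EOT has its own row and its own 35-day PAP.

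Section 7.2.4 describes the diary schedule twice. It lists collection cycles ("Week 57 to the Week 65 visit, Week 71 to the Week 78 visit, Week 85 to the Week 91 visit, and Week 98 to"; this last cycle ends at Week 104), and it lists gaps without collection, "Week 53 - 57, Week 66 - 70, Week 79 - 84 and Week 92 - 97".

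By-visit analgesic use is computed over each visit's own PAP (7.2.4). In 7.3.3, "Proportion of patients not using protocol-specified analgesics for endometriosis-associated pain at Week 52, and Week 104/EOT will be presented" by treatment group and by visit, and the no-opioid proportion is handled in the same way. Neither section defines not using, and neither allows for window length.

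**The concern.** A proportion with no use depends on how long patients are watched. With complete diaries, adding days can only leave it unchanged or lower it. It falls as soon as some women take analgesics intermittently, which is to be expected because section 2.1 allows rescue analgesics for control of pain and not prophylactically.

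The length changes between the Week 52 and Week 65 rows, which is where a reader of a long-term extension looks for loss of effect. A drop produced by the window would look like waning. In addition, the same completer can count as a user at Week 104 and a non-user at Week 104/EOT if her only pills fall in the earlier part of the longer window.

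**Working it through.** **1. Window lengths in Table 11** (offset + 1):

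- Week 52: 34 + 1 = 35 days
- Week 65: 56 + 1 = 57 days (57/35 = 1.63 times Week 52)
- Week 78: 56 + 1 = 57 days (1.63)
- Week 91: 48 + 1 = 49 days (1.40)
- Week 104: 51 + 1 = 52 days (1.49)
- Week 104/EOT: 34 + 1 = 35 days

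Exceptions before Week 52: Week 4 runs from Day 1 to Day 29, so 29 days. For Week 28, X − 34 = 197 − 34 = 163, but the window starts at the first extension dose. A start on Day 169–171 leaves 29–27 days; a start on Day 180 leaves 197 − 180 + 1 = 18.

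**2. Lengths from the text of 7.2.4**, using Table 3 target days 456, 547, 638 and 731.

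| Visit | Table 11 | Gap list: first day after gap (400, 491, 589, 680) | Cycle text: start on day 7w + 1 (400, 498, 596, 687) |
|---|---|---|---|
| 65 | 57 | 57 | 57 |
| 78 | 57 | 57 | 50 |
| 91 | 49 | 50 | 43 |
| 104 | 52 | 52 | 45 |

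Counting Week 104 as day 7 × 104 + 1 = 729 gives 43 instead of 45 in the last column. The three sources do not agree exactly, and Week 57 appears both in the gap list and as the start of a collection cycle. Because footnote g limits the window to days inside the cycle, the effective length depends on which description is used. Every reading exceeds 35 days, and the shortest is 43.

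**3. Effect of length on a zero-use proportion.** The SAP gives no use rates, so these are assumptions. Set P₀(35) = 0.75, the proportion with no use in 35 days.

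- Evenly spread use (Poisson): P₀(L) = 0.75^(L/35).
- Clustered use (gamma-Poisson): P₀(L) = (1 + Lθ)^(−k), with θ chosen so that P₀(35) = 0.75; k = 0.3 is clustered and k = 0.1 extremely clustered.

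| Days | Poisson | k = 0.3 | k = 0.1 |
|---|---|---|---|
| 35 | 75.0% | 75.0% | 75.0% |
| 49 | 66.8% | 70.2% | 72.6% |
| 52 | 65.2% | 69.3% | 72.2% |
| 57 | 62.6% | 68.0% | 71.6% |

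At 57 days the shift is thus about 12, 7 or 3 points.

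Other assumptions widen the range:

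- Identical patients with a 2% daily chance of use: 0.98^35 = 49.3% against 0.98^57 = 31.6%, about 18 points.
- 70% never-users and 30% intermittent users, set to 80% use-free at 35 days: the intermittent users are 0.10/0.30 = 1/3 use-free, so 57 days gives 0.70 + 0.30 × (1/3)^(57/35) = 75.0%, 5 points.
- Only never-users and daily users: no change.

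**4. Missed entries.** If 95% of 35 days are completed, 33.3 days are seen; if 60% of 57 are completed, 34.2 days are seen. Poorer completion later could cancel the effect.

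**5. Week 52 against Week 104/EOT:** 35 against 35 days, so length contributes 0 points.

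**The case against.** The strongest reply is that the comparison which matters is already matched. Section 7.3.3 names Week 52 and Week 104/EOT, both with 35-day PAPs, and so do the primary responder endpoints. This stands. A reader might infer that the extension's main evidence on persistence is compromised; the documents do not support that. Only the by-visit series is affected.

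A reader might also infer that the curves are bound to step down after Week 52. That is too strong. The size rests on use rates the SAP does not give, use for menstrual pain is partly cyclic and 35 days already covers a typical 28-day cycle, and missed entries work the other way. Reading not using as zero pills throughout the PAP is itself an inference, although a natural one.

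The same argument might be extended to the subject modified Biberoglu and Behrman (sB&B) dysmenorrhea score, where a woman reporting no menstruation "for all days of the pain assessment period, then the mean sB&B score will be imputed as 0" (7.3.5). There the objection largely succeeds: the rule follows a sentence about the Week 52 and Week 104/EOT PAPs, both 35 days, and reaches Weeks 65–104 only because 7.3.5 later presents the scores by visit.

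Finally, the windows are openly stated, all analyses are descriptive, and using every collected diary day is defensible for averages. True, but it does not make a zero-use proportion comparable across unequal windows. The SAP itself keeps the bleeding summaries at 28 days through Week 104 (9.3.7) and drops 56-day amenorrhea after Week 52 because some cycles are too short (9.3.8).

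**Conclusion.** The concern holds for the by-visit no-analgesic and no-opioid proportions at Weeks 65, 78, 91 and 104. By Table 11 their windows are 1.40 to 1.63 times the Week 52 window, so, with complete diaries and some intermittent use, they tend to be lower from length alone. The size cannot be fixed from the SAP: about 3 to 12 points at 57 days if 75% are use-free over 35 days, with a wider range from 0 to about 18 points under the other assumptions shown.

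The primary responder endpoints and the Week 52 versus Week 104/EOT contrast are not affected, and average pill counts and mean pain scores are not biased in this way. No test or error rate is involved. The point is minor to moderate: these are descriptive secondary series, but a drop at the Week 52/65 boundary invites misreading. The disagreement between Table 11, the cycle text and the gap list is a separate, smaller defect to be cleared up at the same time.

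**What to change.** - In 7.2.4, 7.3.3 and Table 11, compute the by-visit no-analgesic and no-opioid proportions at Weeks 65, 78, 91 and 104 over the last 35 days of each collection cycle. Every cycle has at least 43 days on any reading, so this is always available, and it removes the length effect for complete diaries.
- State in 7.3.3 what not using means, for example no recorded pills on any day of the PAP.
- If the sB&B dysmenorrhea mean is presented at those visits, use the same 35-day window for both the mean and the zero rule. Applying 35 days to the zero rule alone could score 0 for a woman with recorded pain earlier in the cycle.
- Reconcile the cycle dates, the gap list and the Table 11 offsets.
- Mean pain scores and average pill counts may keep the full cycle. Footnote the shorter windows at Weeks 4 and 28.

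The cost is SAP wording and one programming change, with no new data. By Table 11, 49 − 35 = 14 to 57 − 35 = 22 diary days per cycle go unused for these outcomes.
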